7 MEASUREMENTS AND EVALUATIONS

7.1 Efficacy Measurements

7.1.1 Barry-Albright Dystonia Scale

Dystonia is a neurological movement disorder in which sustained muscle contractions cause twisting and repetitive movements or abnormal postures. The Barry-Albright Dystonia (BAD) scale is a reliable and responsive measure for rating the degree to which dystonia interferes with function (27). A 5-point ordinal scale is used to rate the severity of dystonia in 8 body regions: eyes, mouth, neck, trunk, and each upper and each lower extremity. The individual scores are then summed to provide a total score that ranges from 0 to 32; the higher the score, the more severe the dystonia. See [Appendix 4](#).

For study TIRCON2012V1, a protocol was prepared by a group of experts to define a standardized way to administer and read the BAD scale, including a provocation test to better capture episodic or non-continuous symptoms. The administration of the BAD scale by the investigator or delegate is videotaped, and the videotape is sent to a central evaluator for objective assessment. The results will be sent back to the site, and will be entered by the study site staff into the eCRF.

In study TIRCON2012V1-EXT, the BAD scale will be administered at Visits 1, 2, 3, and 4 (or early termination visit).

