7.2 Safety Measurements

7.2.1 Adverse Events and Serious Adverse Events

7.2.1.1 Definition of Adverse Events

An adverse event (AE) is any untoward medical occurrence in a patient who is administered a pharmaceutical or other therapeutic product in a clinical study, not necessarily having a causal relationship with the product. An AE can therefore be any unfavorable and unintended sign, symptom, or disease temporally associated with the use of a product, whether or not considered related to that product.

AEs include:

- Exacerbation of a pre-existing illness, including acute episodes/crisis of a chronic underlying condition
- An increase in frequency or intensity of a pre-existing episodic event or condition
- A condition detected or diagnosed after study treatment administration, even though it may have been present prior to the start of the study
- A continuous persistent disease or symptom present at baseline that worsens following the start of the study
- Accidents (e.g., involving a motor vehicle)
- Reasons for changes in concomitant medication (type of drug and/or dose)
- Medical, nursing, or pharmacy consultation
- Admission to hospital and surgical operations
- Abnormalities in laboratory findings (e.g., blood chemistry, hematology, urinalysis), ECG, or other assessments (e.g., vital signs) that are not part of a larger medical condition already recorded as an AE and which are judged by the investigator to be clinically significant. The investigator should exercise medical and scientific judgment in deciding whether an abnormal laboratory finding or other abnormal assessment is clinically significant.

AEs do not include:

- A pre-existing disease or condition present or detected at the start of the study that does not worsen
- Hospital admissions or surgical procedures that had been planned prior to enrolment into the study

- The disease or disorder being studied, or a sign or symptom associated with that disease or disorder, unless it has worsened
- An overdose of either the study treatment or concurrent medication without any signs or symptoms

Note: A case of overdose that is not associated with an AE is to be documented as a protocol deviation and promptly reported to the Medical Monitor.

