3.5 Missing Data Handling and Derivation Rules

For safety data analysis, no imputation will be performed on the missing data and analysis will be based on observed cases.

For efficacy endpoints, the continuous variables will be summarized and analyzed as recorded on the case report forms (CRFs). If statistically significant imbalances are detected in the incidence of changes in DBS settings and outcome impacting medication use as well as the frequency of PRN drug or rescue medication between the initial study and the extension study, a Mixed-Effect Model Repeated Measure (MMRM) model will be used as the analysis method to compare the change in score from baseline between the initial study and the extension study for patients who received placebo in initial study (TIRCON2012V1) and the analysis will be based on observed cases. If no significant imbalance was detected, the paired t-test will be used as the analysis method and the last observed data will be used.

For the efficacy analysis on all patients who received DFP during the initial and the extension study, the last observation will be used to calculate the change from baseline for patients terminated early. As a sensitivity analysis, for early termination due to worsening of disease conditions or inadequate efficacy of the drug, as indicated in the CRF, the “worst score” method will be used for data imputation. That is, for continuous variables such as BAD total score at a particular time point, the worst score of all patients will be used to impute the missing data at that time point. For categorical variable such as responder, the worst category (treatment failure) will be assigned. For missing data due to missed visit, the last observation will be used to fill the void.

For BAD total score, if one or several component scores cannot be measured, then the same component score from the last visit will be carried forward and if it is also missing, the score from the next visit will be carried backward to fill the missing component score(s) before the total score is calculated.

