4.3.2 Exploratory Analyses/Sensitivity Analysis

In order to explore potential differences in the change in BAD from baseline to Visit 4 and PGI-I at Visit 4 across population subgroups, subgroup analyses will be performed for the ITT population on the following factors assessed at the baseline of the initial study: Age at onset of motor symptoms (<6 years vs. ≥ 6 years), DBS (Deep Brain Stimulation, Yes vs. No), Region (US vs. Europe), and Duration of disease (>5 years vs. ≤ 5 years).

Besides analysis for the ITT population, the efficacy analyses will also be repeated for outcomes defined based on BAD total score and PGI-I for the PP population as sensitivity analyses.

As a sensitivity analysis, the statistical analysis on the change in the BAD total score from baseline to Visit 4 and PGI-I at Visit 4 will be repeated with the missing data being imputed as described in section 3.5 based on the ITT population.

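### The worst-score sensitivity imputation in SAP 3.5 has no floor at the patient's own score and a narrow trigger, so it can be milder than last observation for some patients and miss others

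*SAP*

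**What the plan says.** The main rule for the all-patient efficacy analysis (SAP 3.5) is that "the last observation will be used to calculate the change from baseline for patients terminated early".

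The sensitivity rule in the same section applies "for early termination due to worsening of disease conditions or inadequate efficacy of the drug, as indicated in the CRF". For continuous variables such as the BAD total score, "the worst score of all patients will be used to impute the missing data at that time point". For responder status the rule is different: "For categorical variable such as responder, the worst category (treatment failure) will be assigned".

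SAP 4.3.2 says where the imputation is used: the analyses of BAD change to Visit 4 and of PGI-I at Visit 4 "will be repeated with the missing data being imputed as described in section 3.5 based on the ITT population".

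The BAD scale gives a "total score that ranges from 0 to 32; the higher the score, the more severe the dystonia" (Protocol 7.1.1). Visit 4 is month 36 for patients on deferiprone in both studies and month 18 for patients switched from placebo (SAP section 4).

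On withdrawal reasons, the shell of SAP Table 14.1.5 has one row for adverse event and another for worsening of disease or lack of efficacy. It has no row for death. Protocol 7.2.1.1 counts as an adverse event: "Exacerbation of a pre-existing illness, including acute episodes/crisis of a chronic underlying condition".

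**The concern.** A worst-score analysis shows whether a result survives a harsh assumption about patients who left because they were doing badly. For that, it should never treat such a patient more kindly than the main analysis does. The SAP rule does not ensure this. The imputed value comes from other patients' scores at the time point, and the withdrawn patient, who may have been the most severe, has no score there.

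The trigger has a separate weakness. It depends on the withdrawal reason in the CRF, and the protocol lets disease exacerbation be an adverse event. Two patients with the same deterioration can therefore be handled differently according to which reason was entered. The rule does not mention patients who die.

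At stake is how far the sensitivity result for the Visit 4 BAD change, and for PGI-I, can be read as a pessimistic bound.

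**Working it through.** The documents give no figure to reproduce here: no BAD distribution, no expected number of such withdrawals and no formal sample size calculation. The check is therefore logic and small arithmetic, with illustrative scores on the 0 to 32 scale.

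**Notation.** B = the patient's baseline, L = last observed score, M = own worst observed score (baseline included), W = worst score of all patients at the time point. Higher is worse.

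- Main analysis: change = L - B.
- SAP worst-score rule: change = W - B.
- Difference, sensitivity minus main: W - L.

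The sensitivity value is milder than the main one when L > W. It credits an improvement when B > W. For a patient who left after worsening (L at or above B), the second condition is the stricter one.

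**Is the patient outside the pool?** The SAP section 4 windows classify efficacy scores by time since first exposure: 33 to <39 months for month 36, and 15 to <21 for month 18. BAD is recorded at early termination (Protocol Table 5.1). If the exit score falls inside the Visit 4 window, nothing is missing. If it falls before the window, it is not a Visit 4 score. So, with scores tied to visits in this way, a patient who needs imputing at Visit 4 does not contribute to W.

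**Examples** (M = L assumed; last column is the proposed floor, max(W, M) - B)

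| B | L | W | Last observation | SAP worst score | With floor |
|---|---|---|---|---|---|
| 28 | 30 | 26 | 30 - 28 = +2 | 26 - 28 = -2 | 30 - 28 = +2 |
| 28 | 30 | 29 | +2 | 29 - 28 = +1 | 30 - 28 = +2 |
| 24 | 28 | 31 | 28 - 24 = +4 | 31 - 24 = +7 | 31 - 24 = +7 |

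Row 1 credits an improvement. Row 2 only shrinks the worsening. Row 3 works as intended, and the floor leaves it alone.

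**Effect on the mean.** With k imputed patients among N and a common W, the sensitivity mean differs from the main mean by (k/N) x (W - mean of their last scores). It is milder overall only if the mean last score of the imputed patients exceeds the worst score of everyone in the pool.

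- Row 1 as the only imputed patient: (26 - 30)/N. This is -4/68 = -0.06 for all 68 enrolled, -4/44 = -0.09 for the 44 on deferiprone throughout, and -4/24 = -0.17 for the 24 switched from placebo (SAP 3.2; all before dropout).
- Add a second imputed patient with last score L2. The sum is (26 - 30) + (26 - L2), which is positive, hence harsher than last observation, whenever L2 < 22.

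One milder patient among those imputed is therefore enough to reverse the direction. The mean turns milder mainly when the pool is small and those who leave are the most severe.

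**Trigger.** Set side by side, SAP 3.5 requires worsening or inadequate efficacy as the CRF reason, Table 14.1.5 offers adverse event as a different reason, and Protocol 7.2.1.1 makes exacerbation an adverse event. A deterioration entered in the adverse-event row does not meet the trigger. Nor does a death, unless it is entered as worsening. Both then keep last observation.

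**The case against.** The strongest reply is that the SAP says all patients, not patients still under assessment. If the worst score were taken over all visits, the withdrawn patient's own score would be in the pool and the problem would vanish. That reading is possible. However, the sentence names the time point twice, so the visit-specific reading is the natural one. The SAP also does not say whether the Visit 4 pool is month 18, month 36 or both. The ambiguity itself justifies a clarifying sentence.

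Second, a reader might infer that the sensitivity analysis as a whole tends to be kinder than the main one, or routinely credits improvement. The documents do not support that. Most imputed patients would be pushed up to the worst score in the pool, and for mild patients that is a large penalty. This reply stands.

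Third, a reader might infer that nothing else tests the Visit 4 result. That is also wrong. The responder rule makes these patients failures whatever score is imputed. There is also a per-protocol repeat and a longitudinal BAD model, although the former excludes early terminators and the latter estimates a slope. One caution: SAP section 5 lists the imputed responder table (14.2.1.16s) under the per-protocol population, which contains no early terminators. SAP 4.3.2 specifies ITT for the imputed BAD-change and PGI-I analyses, so the title may be a slip.

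Fourth, Table 14.1.5 has a dedicated worsening row, and nothing shows that such withdrawals are being entered as adverse events. True: the documents show only that they can be.

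**Conclusion.** The point holds in a limited form. On the visit-specific reading, SAP 3.5 allows a patient who left for worsening to be imputed better than his or her last observation and, more rarely, better than baseline. For PGI-I the imputed value can likewise fall below the patient's own last rating, but improvement would be credited only if every patient scored at that time point rated below 4 (no change).

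The effect is on individual patients. In the worked example it is 4 points for one patient, or less than 0.1 point in the mean of 44 or 68. A milder mean requires the imputed patients' average last score to exceed the worst score in the pool. How often that would happen cannot be derived from the documents, because the score distribution and the withdrawals are not given.

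The missing floor leaves the last-observation main analysis and the responder analysis untouched. The narrow trigger follows directly from the text and needs no assumed distribution. This is a cheap improvement to a sensitivity analysis of secondary endpoints in a safety extension. It is not a flaw in the main result.

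**What to change.** Keep the SAP rule and add to section 3.5:

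- **Floor.** Impute the larger of (a) the worst score of all patients at that time point and (b) the patient's own worst observed score, baseline included. Since max(W, M) is at least M, and M is at least L and B, the result can never be milder than last observation or show an improvement.
- **Trigger.** Apply the rule also to deaths and to withdrawals for an adverse event recorded as PKAN-related. Protocol 7.2.1.2 already has disease-related events recorded separately, so these withdrawals should be identifiable. The treatment-failure rule for responders depends on the same condition and would widen with it.
- **Pool.** State which patients and visits supply the worst score, given that Visit 4 is month 18 for one group and month 36 for the other.

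The floor and trigger need about one sentence, and the pool definition a clause more. No new data are needed. The downside is a slightly less favourable sensitivity result.

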Study design:	
Study TIRCON2012V1-EXT is an 18-month, multi-center, single-arm, open-label extension of study TIRCON2012V1. In the initial study, patients with a diagnosis of PKAN are being randomized in a 2:1 ratio to receive 18 months of treatment with either deferiprone or placebo, respectively. All participants who complete TIRCON2012V1 will be offered the opportunity to continue in the extension study, with the final visit (Week 78) of the initial study being considered Visit 1 of the extension study. (A 4-week follow-up visit that is planned for the end of study TIRCON2012V1 will be cancelled for individuals who choose to continue.)
 
Patients who were randomized to receive deferiprone in study TIRCON2012V1 will continue to receive deferiprone in the extension study, while those who were randomized to receive placebo will be switched to deferiprone. Since the initial study will still be in progress at the time that the first patients enter the extension study, patients and study staff will remain blinded as to which product was received for the previous 18 months.
 
In order to minimize the possible gastrointestinal upset that could result from starting deferiprone at too high a dose (and which might alert the former placebo recipients to the change in product), the dosing regimen will be titrated weekly for the first 3 weeks. All patients, including those who were on deferiprone initially, will receive 5 mg/kg deferiprone twice a day (b.i.d.) for the first week. If this dose is tolerated and there are no signs of toxicity, the dose will be increased to 10 mg/kg b.i.d. for the next week; and if that dose is tolerated, it will be increased the following week to 15 mg/kg b.i.d. for the remainder of the study. Individual dosages may be adjusted downward if necessary at any time for reasons of safety or tolerability.
	

Name of Sponsor: ApoPharma Inc.	Individual Study Table Referring to Part of the Dossier Volume: Page:	(For National Authority Use Only)
Name of Finished Product: Deferiprone		
Name of Active Ingredient: 3-hydroxy-1,2-dimethylpyridin-4-one		
Study design (cont'd):	Patients will have their hematology blood counts monitored weekly, and will undergo safety and efficacy assessments at 6 months (Visit 2), 12 months (Visit 3), and 18 months (Visit 4).	
Duration of participation:	The duration of participation in the extension study for each patient will be approximately 18 months.	

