3.1 Study Design

Study TIRCON2012V1-EXT is an 18-month, multi-center, single-arm, open-label extension of study TIRCON2012V1. In the initial study, patients with a diagnosis of PKAN were being randomized in a 2:1 ratio to receive 18 months of treatment with either deferiprone or placebo, respectively. All participants who completed TIRCON2012V1 were offered the opportunity to continue in the extension study, with the final visit of the initial study being considered Visit 1 of the extension study. Patients who had been randomized to receive deferiprone in study TIRCON2012V1 continued to receive deferiprone in the extension study, while those who had been randomized to receive placebo were switched to deferiprone. Since the initial study were still in progress at the time that the first patients entered the extension study, patients and study staff remained blinded until the initial study was over as to which product was received for the previous 18 months.

In the TIRCON-EXT study, patients will have their hematology blood counts monitored weekly, and will return to the study site at 6 months (Visit 2), 12 months (Visit 3), and 18 months (Visit 4) for assessments of safety and efficacy.

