Date of exposure will be defined as day 1 for all duration calculations. For example, age at entry will be calculated as the integer value of the expression: (date of exposure – date of birth) / 365.25. For patients on DFP in the initial study, the date of exposure during the initial study (TIRCON2012V1) will be used while for those switched from placebo to DFP in the extension study (TIRCON2012V1-EXT), the date of exposure during the extension study will be used.

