14.1 Disposition, Demographics and Baseline Data

Table 14.1.1	Number of patients in different populations
Table 14.1.2	Subject disposition – ITT population
Table 14.1.3	Subject exposure to study medication – ITT population
Table 14.1.4	Number of patients enrolled by study site – ITT population
Table 14.1.5	Summary of the reasons for not completing the study – ITT population
Table 14.1.6	Summary of demographics data at baseline of initial study – ITT population
Table 14.1.6a	Summary of demographics data at baseline of initial study – PP population
Table 14.1.7	Summary of baseline characteristics at the initial study – ITT population
Table 14.1.7a	Summary of baseline characteristics at the initial study – PP population

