Completed	xx	xx	xx
Withdrawn	xx	xx	xx

Table 14.1.3 Subject exposure to study medication – ITT population

	Group		
	Placebo-DFP (N=xx)	DFP-DFP (N=xx)	Overall (N=xx)
Subjects Exposed	xx	xx	xx
Total Exposure (person-years)	xxx.x	xxx.x	xxx.x
Length of Exposure (years)			
Mean (SD)	xx.xx (xx.x)	xx.xx (xx.x)	xx.xx (xx.x)
Median	xx.x	xx.x	xx.x
(Min, Max)	(xx.x, xx.x)	(xx.x, xx.x)	(xx.x, xx.x)
Duration of Exposure [n(%)]			
>= 1 month	xx (xx)	xx (xx)	xx (xx)
>= 6 months	xx (xx)	xx (xx)	xx (xx)
Repeat for 9, 12, 15, 18 months

Table 14.1.4 Number of patients enrolled by study site – ITT population

Country	Site	Group		
		Placebo-DFP	DFP-DFP	Overall
xxx	000x	xx	xx	xx
...	...	xx	xx	xx
Total	x	xx	xx	xx

Table 14.1.5 Summary of the reasons for not completing the study – ITT population

		Group		
		Placebo-DFP (N=xx)	DFP-DFP (N=xx)	Overall (N=xx)
Reason	Detail	n (%)	n (%)	n (%)
Adverse event	Ccccc	xx (xx)	xx (xx)	xx (xx)
	Ccccc	xx (xx)	xx (xx)	xx (xx)
Voluntary withdrawal	Ccccc	xx (xx)	xx (xx)	xx (xx)
	Ccccc	xx (xx)	xx (xx)	xx (xx)
Lost to follow up	Ccccc	xx (xx)	xx (xx)	xx (xx)
	Ccccc	xx (xx)	xx (xx)	xx (xx)
Investigator decision	Ccccc	xx (xx)	xx (xx)	xx (xx)
	Ccccc	xx (xx)	xx (xx)	xx (xx)
Protocol violation	Ccccc	xx (xx)	xx (xx)	xx (xx)
	Ccccc	xx (xx)	xx (xx)	xx (xx)
Worsening of the disease/ Lack of efficacy	Ccccc	xx (xx)	xx (xx)	xx (xx)
	Ccccc	xx (xx)	xx (xx)	xx (xx)
Other	Ccccc	xx (xx)	xx (xx)	xx (xx)
	Ccccc	xx (xx)	xx (xx)	xx (xx)
Total		xx (xx)	xx (xx)	xx (xx)

Demographics and baseline characteristics tables

Table 14.1.6 Summary of demographics data at baseline of initial study – ITT population

	Group			
	Placebo-DFP (N=xx)	DFP-DFP (N=xx)	Overall (N=xx)	DFP vs Placebo p -value [§]
Age (years) (Mean ± SD) (Minimum, Median, Maximum)	xx.x ± xx.x (xx.x, xx.x, xx.x)	xx.x ± xx.x (xx.x, xx.x, xx.x)	xx.x ± xx.x (xx.x, xx.x, xx.x)	0.xxxx
Sex: n (%) Female Male	xx (xx) xx (xx)	xx (xx) xx (xx)	xx (xx) xx (xx)	0.xxxx
Racial Origin: n (%) White Black Asian Native American Native Hawaiian or Other Pacific Islander Multi-Racial	xx (xx) xx (xx) xx (xx) xx (xx) xx (xx) xx (xx)	xx (xx) xx (xx) xx (xx) xx (xx) xx (xx) xx (xx)	xx (xx) xx (xx) xx (xx) xx (xx) xx (xx) xx (xx)	0.xxxx
Ethnic Origin: n (%) Hispanic/Latino Other	xx (xx) xx (xx)	xx (xx) xx (xx)	xx (xx) xx (xx)	0.xxxx

§ T-test for means and Fisher's exact test for percentages

Similar Table 14.1.6a will be based on PP population

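### The SAP's only age rule dates Placebo-DFP patients about 18 months later than DFP-DFP patients, but Tables 14.1.6 and 14.1.6a present and test age as of the initial-study baseline

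*SAP*

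**What the plan says.** SAP section 3.5 contains the only derivation of age in the plan. It states that "age at entry will be calculated as the integer value of the expression" obtained by subtracting date of birth from date of exposure and dividing by 365.25. It then sets the exposure date by group. The sentence starts with those who already took deferiprone before the extension and reads in part "the date of exposure during the initial study (TIRCON2012V1) will be used while for those switched from placebo to DFP in the extension study". For the switched patients it goes on to name the extension exposure date.

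The SAP list of tables (section 5) and the table shells (section 7) define the output: "Table 14.1.6 Summary of demographics data at baseline of initial study", with a per-protocol repeat numbered 14.1.6a. The shell has an age row in years, columns for Placebo-DFP, DFP-DFP and Overall, and a p-value column comparing DFP with placebo. Its footnote assigns a t-test to means, which covers age.

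SAP section 4.2.1 lists age among the demographics to be summarised and gives no other reference date. On the gap between the two dates, SAP section 3.1 describes patients "randomized in a 2:1 ratio to receive 18 months of treatment with either deferiprone or placebo", and the protocol synopsis places the start of the extension "with the final visit (Week 78) of the initial study being considered Visit 1 of the extension study".

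**The concern.** The rule measures age at a different point in the two columns. For DFP-DFP patients, first deferiprone exposure coincides with the start of the initial study, so the age matches the table title. For Placebo-DFP patients, it comes after a full course of placebo, so the age belongs to a visit about 18 months after the time point named in the title.

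The table then tests one column against the other, so part of any difference tested would come from the calendar and not from the patients. A reader who uses this row to judge whether the two groups are alike at the outset would see an age gap that is too large if Placebo-DFP patients are truly the older group. The gap could be masked if they are truly the younger.

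**Working it through.** The documents give no age figure to reproduce. The check sizes the offset and its effect on the row.

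**Inputs**
- Initial-study length: 78 weeks (protocol synopsis); 18 months (SAP 3.1).
- Enrolled: 24 former placebo and 44 former deferiprone patients, 68 in total (SAP 3.2). ITT and PP counts are not given and may be smaller.
- Significance level: two-sided 0.05 (SAP 3.6).
- Age SD: not in the documents. Assumed 6, 10 or 15 years.
- Assumed timing: first initial-study dose at its baseline, and first extension dose at extension Visit 1.

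**Offset.** 78 × 7 / 365.25 = 1.495 years, or 17.9 months.

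**Effect of taking the integer part.** Adding 1.495 years raises a whole-year age by either 1 or 2. If birthdays are spread evenly over the year, it rises by 2 with probability 0.495 and by 1 otherwise. The mean rise is 0.505 × 1 + 0.495 × 2 = 1.495 years. Truncation does not remove the offset.

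**Overall mean.** 24/68 × 1.495 = 0.53 years too high.

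**Between-group test.** The standard error of the difference is SD × √(1/24 + 1/44) = SD × 0.2538. The shift in the t statistic is 1.495 divided by that. The last column is the chance of p < 0.05 if the two groups truly had the same mean age at initial-study baseline (noncentral t, 66 df).

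| Assumed SD (years) | Standard error | Shift in t | Chance of p < 0.05 |
|---|---|---|---|
| 6 | 1.52 | 0.98 | 16% |
| 10 | 2.54 | 0.59 | 9% |
| 15 | 3.81 | 0.39 | 7% |

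With both groups aged at the same initial-study date, the built-in difference is zero and the rejection rate returns to 5%.

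**Where this age is used.** The comparative MMRM in SAP section 4 contains treatment, visit, their interaction, baseline score, DBS change, medication use and PRN/rescue frequency. The trend model contains time only. Neither includes age. The age-related subgroup in SAP 4.3.2 is age at onset of motor symptoms, a different variable. The trigger for covariate adjustment in SAP 3.5 and section 4 concerns DBS settings and medication use, not demographics.

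**The case against.** The strongest reply is that the rule may be deliberate and the title loose. The protocol and SAP define the efficacy baseline as the point before deferiprone starts, which for former placebo patients is extension Visit 1. Age at first deferiprone exposure fits the pooled on-deferiprone analyses. This stands as a reason to keep that variable. It does not rescue a table that names the initial-study baseline.

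A second reply is that section 3.5 defines age at entry as an example within a general rule on durations, while the shell row says only age in years. A programmer guided by the title could produce the right ages. That is possible, so it is not established that the reported figures will be wrong. But no written rule provides for that reading, and a correct table would mean departing from the only rule there is.

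Two stronger readings are tempting. One is that the offset would suggest a false imbalance between the randomised arms. The documents do not support this. The columns hold extension enrollees: of 89 randomised, 76 completed and 68 enrolled, and the ITT set further requires a post-baseline assessment. Even with correct ages, the p-value would not test the randomisation. The offset can also hide a difference as easily as suggest one.

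The other is that efficacy or safety conclusions are affected. None of the planned models or tests uses this age, and the comparisons of the placebo and deferiprone periods are within patient.

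**Conclusion.** The conflict is real and minor. For Placebo-DFP patients, the age rule in SAP 3.5 and the title of Tables 14.1.6 and 14.1.6a cannot both be followed, and the SAP does not say which governs. If the rule governs, the Placebo-DFP mean age is about 1.5 years too high for the stated time point, the Overall mean is about 0.5 years too high, and the p-value compares ages taken at different points.

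The 1.5 years rests on the 78-week design and the assumed dose timing. The Overall figure and the t shift of about 0.4 to 1.0 also rest on enrolled counts, and the t shift on an assumed SD of 15 to 6 years; the per-protocol table will have different, unknown numbers. Each shift in that range is below one standard error, so false significance is possible but not likely. The consequence is confined to the age row of two descriptive tables.

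**What to change.** Add one sentence to SAP 3.5 or 4.2.1: for Tables 14.1.6 and 14.1.6a, age is computed at the first dose of TIRCON2012V1 study medication, whether deferiprone or placebo, in both groups. If age at first deferiprone exposure is wanted for the on-deferiprone analyses, keep it as a second variable with its own label.

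The change needs only dates of birth and first-dose dates from the initial study, so it requires no new data and alters no other planned analysis. Because section 3.5 applies the same day 1 to every duration, the same edit could state the reference date for disease duration in Table 14.1.7, which is also labelled as initial-study baseline.
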